#### 2.2.4 Proton-based Short Course Radiation Therapy for pancreatic cancer: MGH Experience

The safety and efficacy of a one-week course of preoperative proton beam therapy and capecitabine followed by early pancreaticoduodenectomy (PD) was explored in a prior study in our institution in a different study population. Patients with radiographically resectable, biopsy-proven pancreatic cancer of the head of the pancreas were enrolled from May 2007-March 2010 on this IRB-approved, NCI-sponsored clinical trial. Eligibility included no CT involvement of the SMA or celiac arteries; adequate renal, hepatic and hematopoietic function; and ECOG PS 0/1. Dose level 1 consisted of PBT delivered 3 Gy x 10 Monday to Friday. Pts in subsequent dose levels received 5 Gy x 5 in progressively shortened schedules: level 2 (wk 1 M W F, wk 2 T Th), level 3 (wk 1 M T Th F, wk 2 M), level 4 (wk 1 M-F). Proton beam therapy was targeted at pancreatic mass with elective nodal coverage. Pts received Capecitabine 825 mg/m^2 BID wk 1 and 2 M-F. Surgery was performed 1-6 wks after completion of chemotherapy. Patients were recommended to receive 6 months of gemcitabine after surgery. 31 pts were enrolled on study. 27 patients are eligible for this analysis. Three patients were treated at each of dose levels 1-3. Six patients were at dose level 4, which was selected as the MTD. No dose limiting toxicities were observed. There were no unexpected 30-day post-op complications noted in comparison to historical controls. 4/21 resected patients had positive margins. 17/21 had positive nodes. Median follow up is 10 months. There have been 2 local failures/progression in ALL patients, both with synchronous metastatic disease (at 10 mo and 17 mo). Metastatic failure has occurred in 15 out of 27 patients (56%). In summary, we found pre-operative CRT with 1 week of PBT and capecitabine followed by early surgery feasible and associated with satisfactory local control.

#### 2.2.5 Photon based short course chemoradiation in locally advanced pancreatic cancer

Dholakia and colleagues have studied fractionated stereotactic body radiation therapy (SBRT) of 33 Gy photons in five fractions for locally advanced pancreatic cancer. They demonstrated local control of 83% at one year with minimal acute or late gastrointestinal toxicity and favorable survival compared to historical data. (33) This correlates well with our five fraction proton studies.

#### 2.2.6 Summary

This research study combines several key tenets. First, we hypothesize that pre-radiation FOLFIRINOX therapy will optimize the treatment of patients with locally advanced pancreatic adenocarcinoma based on its superior response rate demonstrated in patients with advanced pancreatic cancer in the Prodiges-4/ACCORD trial. Based on compelling preclinical data regarding Losartan's many potential synergistic benefits in angiogenesis inhibition and collagen matrix stabilization, we posit that the addition of this agent will further potentiate the benefit of FOLFIRINOX therapy via enhanced drug delivery. The subsequent use of radiation therapy aims to consolidate upfront chemotherapy treatment in an effective manner, with tolerable toxicity.

### **2.3 Patient-reported outcomes (PRO) background**

There are few published studies measuring patient-reported symptoms and quality of life (QOL) outcomes in patients with pancreatic cancer. Most of the existing studies assessing QOL in patients with pancreatic cancer are focused on individuals with advanced disease.[30, 31] The few studies that have included patients with operable pancreatic cancer included small sample sizes in heterogeneous patients.[32, 33] Despite the fact that depression is a frequently reported symptom in patients with pancreatic cancer, the prevalence among different stages of disease has not been thoroughly investigated.[34] A more detailed and comprehensive understanding of the burdens faced by patients with locally advanced pancreatic cancer will identify areas for clinicians to enhance their supportive care efforts.

Studying patients' symptom burden and QOL while they are participating in a clinical trial provides an opportunity to better understand their disease- and treatment-related outcomes. Patients' symptom burden and QOL are better indicators of their treatment tolerability than clinician-reported toxicity monitoring. Combining objective endpoints, such as response rate, with subjective patient-reported outcomes has become increasingly important in determining efficacy, toxicity, and safety and for allowing comparisons across treatment arms.[35] Additionally, evaluating patient-reported measures may help highlight patients' difficulties with treatment adherence by demonstrating additional side effects and toxicities of therapy.[36] Increased attention to patients' symptom burden and QOL while they are participating in a clinical trial provides an opportunity to improve their quality of care.[37, 38] Thus, we aim to

describe QOL, symptom burden and mood in this study population to help us better identify the side effects and challenges faced by patients with locally advanced pancreatic cancer.

A randomized trial comparing the efficacy of gemcitabine and FOLFIRINOX in metastatic pancreatic cancer also assessed QOL, using the European Organization for the Research and Treatment of Cancer QOL Questionnaire C30 (EORTC QLQ-C30).[31] The authors demonstrated that FOLFIRINOX not only prolonged survival, but also significantly reduced QOL impairment compared to gemcitabine for patients with metastatic cancer. Thus, in addition to the utility of describing the symptom burden and QOL in patients with locally advanced pancreatic cancer, it will also be useful to compare these outcomes in patients receiving different chemotherapy regimens.

We will use the EORTC QLQ-C30, a validated instrument designed for prospective clinical trials that evaluates five functions (physical, role, cognitive, emotional, and social), and nine symptoms (fatigue, pain, nausea and vomiting, dyspnea, loss of appetite, insomnia, constipation, diarrhea, and financial difficulties) to measure QOL.[39] We will use the Edmonton Symptom Assessment System-revised (ESAS-r) to measure symptoms, which has been previously validated in patients with advanced cancer.[40] The ESAS-r consists of ten items assessing pain, fatigue, drowsiness, nausea, anorexia, dyspnea, depression, anxiety, well-being, and a free-response item. We will include constipation as the free-response item. The ten items are scored on a scale of 0-10 (0 reflecting no reported presence of the symptom and 10 reflecting the worst possible severity of the symptom). We will instruct patients that items are to be rated based on the previous 24-hour period. We will use the Hospital Anxiety and Depression Scale (HADS) to assess symptoms of depression and anxiety.[41] The HADS is a 14-item questionnaire that contains two 7-item subscales assessing depression and anxiety symptoms during the past week. The questionnaire consists of a four-point item response format that quantifies the degree to which participants experience a particular emotion. Scores on each subscale range from 0 to 21, with a cutoff of 8 or greater denoting clinically significant depression or anxiety symptoms.

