### **1.3 Secondary Objectives**

- 1.3.1 To determine the progression-free survival of patients with locally advanced disease who receive FOLFIRINOX-Losartan and radiation therapy.
- 1.3.2 To determine overall survival in patients treated with FOLFIRINOX-Losartan and radiation therapy.
- 1.3.3 To determine the overall survival of patients with locally advanced disease who receive FOLFIRINOX-Losartan without radiation (i.e. patients who demonstrate progression at restaging.)
- 1.3.4 To determine the toxicity of FOLFIRINOX – Losartan in patients with locally advanced pancreatic cancer.
- 1.3.5 To determine the toxicity of FOLFIRINOX – Losartan and radiation in patients with locally advanced pancreatic cancer.

- 1.3.6 To determine the rate of downstaging to surgical resection of FOLFIRINOX-Losartan followed by radiation in patients with locally advanced pancreatic cancer.
- 1.3.7 To determine the correlation between a panel of somatic genetic mutations (SNaPSHOT) and outcome in locally advanced pancreatic cancer treated with FOLFIRINOX-Losartan +/- radiation/capecitabine.
- 1.3.8 To determine the correlation between circulating biomarkers of TGF- $\beta$ 1 downregulation, including circulating Collagen I levels, and outcome in locally advanced pancreatic cancer treated with FOLFIRINOX-Losartan +/- radiation/capecitabine.
- 1.3.9 To describe quality of life, symptom burden and mood in the study population.
- 1.3.10 To measure utilization of health services (emergency room, hospital and intensive care unit, palliative care) in the study population.

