### 8.2.1 Patient-reported outcomes

QOL (EORTC QLQ-C30, version 3.0), symptoms (ESAS-r), and mood (HADS) will be assessed at time of informed consent prior to neoadjuvant therapy; at weeks 3, 7, 11, and 15 of neoadjuvant chemotherapy; at week 2 of capecitabine chemoradiotherapy. During the follow up period, these measures will be assessed at the 3 month post-operative follow-up visit, then every 6 months for the first 2 years of follow up, then yearly until completion of year 5. We will include a window of +/- 2 weeks for obtaining the PROs during treatment, to cover timing adjustments for treatment delays. In follow up, these outcomes will be assessed within +/- 21 days of a correlating follow up visit. The patient may complete the questionnaires by hand or over the phone with a study team member, as well as an interpreter (if needed).

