biomarker. Continuous values will be dichotomized at the median or a biologically meaningful threshold. The logrank test will be used to assess differences in progression-free survival and overall survival by biomarker status if at least 5 failure events have been observed within each subgroup. The correlative analysis will be purely exploratory due to the limited numbers expected per biomarker subgroup. In particular, analysis will be descriptive when the frequency of a genetic mutation is low.

14.3.6 ***Patient-reported outcomes***: We will use descriptive statistics to describe QOL (EORTC QLQ-C30), symptom burden (ESAS-r) and mood (HADS) for the entire study cohort. Mean values and standard deviations will be used to describe QOL and symptom burden (T-test or Wilcoxon as appropriate). We will score the HADS subscales for depressive and anxiety symptoms categorically, using a cut-off of >7 to describe the proportion of patients with these symptoms. We will use Chi-square or Fisher's Exact Test, as appropriate, to analyze the categorical variables.

14.3.7 ***Health care utilization***: We will use descriptive statistics to describe hospitalizations, ICU stays, ED visits and palliative care use for the entire study cohort. Mean values and standard deviations will be used to describe continuous variables (T-test and Wilcoxon rank sum, as appropriate). We will use Chi-square or Fisher's Exact Test, as appropriate, to analyze the categorical variables.

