**Please circle the number that best describes how you feel NOW:**

No Pain	0	1	2	3	4	5	6	7	8	9	10	Worst Possible Pain
No Tiredness (Tiredness = lack of energy)	0	1	2	3	4	5	6	7	8	9	10	Worst Possible Tiredness
No Drowsiness (Drowsiness = feeling sleepy)	0	1	2	3	4	5	6	7	8	9	10	Worst Possible Drowsiness
No Nausea	0	1	2	3	4	5	6	7	8	9	10	Worst Possible Nausea
No Lack of Appetite	0	1	2	3	4	5	6	7	8	9	10	Worst Possible Lack of Appetite
No Shortness of Breath	0	1	2	3	4	5	6	7	8	9	10	Worst Possible Shortness of Breath
No Depression (Depression = feeling sad)	0	1	2	3	4	5	6	7	8	9	10	Worst Possible Depression
No Anxiety (Anxiety = feeling nervous)	0	1	2	3	4	5	6	7	8	9	10	Worst Possible Anxiety
Best Wellbeing (Wellbeing = how you feel overall)	0	1	2	3	4	5	6	7	8	9	10	Worst Possible Wellbeing
No _____ Other Problem (for example constipation)	0	1	2	3	4	5	6	7	8	9	10	Worst Possible _____

Patient's Name \_\_\_\_\_

[figure not shown]
[figure not shown]
Date \_\_\_\_\_ Time \_\_\_\_\_

Completed by (check one):

- Patient
- Family caregiver
- Health care professional caregiver
- Caregiver-assisted

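### Section 2.3 and the appended ESAS-r form disagree on the recall period and on item 10, so symptom scores can mix time windows and item 10 can mix symptoms

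*Combined protocol and SAP*

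**What the plan says.** Secondary objective 1.3.9 is descriptive: "To describe quality of life, symptom burden and mood in the study population". Section 2.3 assigns symptoms to the ESAS-r and makes two statements about how it will be given. On recall: "We will instruct patients that items are to be rated based on the previous 24-hour period". On the tenth item: "We will include constipation as the free-response item".

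The ESAS-r form in the appendices opens with its own instruction: "Please circle the number that best describes how you feel NOW". Its tenth line reads "No _____ Other Problem", with the hint "for example constipation" beside it. The worst-possible anchor on that line is also blank.

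On mode, Section 8.2.1 says: "The patient may complete the questionnaires by hand or over the phone with a study team member", with an interpreter if needed. On analysis, Section 14.3.6 says: "Mean values and standard deviations will be used to describe QOL and symptom burden (T-test or Wilcoxon as appropriate".

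**The concern.** A recall period is part of what a symptom item measures. Nausea over the past day and nausea at the moment of asking are different quantities, and they can diverge when symptoms fluctuate around chemotherapy. If some forms are answered under one instruction and some under the other, a cohort mean averages two quantities, and a change between visits may partly reflect a change of instruction. If the instruction a patient followed was not recorded, it cannot be recovered at analysis.

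Item 10 raises a separate problem. A mean of that item describes constipation only if the patients were rating constipation. With a blank line, one patient may rate constipation, another a different problem, and a third may leave it empty.

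Section 2.3 also looks ahead to comparing these outcomes between patients on different chemotherapy regimens. That needs a known and uniform recall period.

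**Working it through.** There is no stated figure to reproduce and no calculation that would size the effect. The check is a comparison of texts.

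**Recall period.**
- Section 2.3: previous 24 hours, by instruction to the patient.
- ESAS-r form: the present moment, printed above the items.
- The form's instruction heads the whole list, so the conflict applies to all ten items.
- For contrast, Section 2.3 gives the HADS a past-week window and the HADS form prints the same, so that instrument is consistent.

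**Item 10.**
- Section 2.3: constipation for every patient.
- ESAS-r form: a blank to be filled, constipation given as an example only.
- This conflict affects one item of ten, and any total that included it. Section 14.3.6 defines no ESAS-r total.

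**Does another section settle it?**
- Section 8.2, its table and Section 8.2.1 fix the timing, the windows and the mode. They do not say that the form is amended, that the blank is pre-filled, or that a spoken instruction overrides the printed one.
- The form has boxes for completion by a family or professional caregiver, which adds further routes by which the instruction can reach the answer.
- Section 14.3.6 gives means and standard deviations, with no rule for the recall period or for item 10 entries that name another symptom.

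**How many assessments.** From the table in Section 8.2: consent (1), Day 1 of cycles 2, 4, 6 and 8 (4), and week 2 of chemoradiation (1). That is 1 + 4 + 1 = 6, plus the post-operative follow-up series to year 5.

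**How much is covered elsewhere at the same visits.** The ESAS-r has nine named items.
- Pain, fatigue, nausea, appetite and dyspnea are also in the QLQ-C30: 5.
- Depression and anxiety are in the HADS: 2.
- So 5 + 2 = 7 of the 9 named items have a counterpart; drowsiness and well-being are the other two.
- Constipation, the intended item 10, is QLQ-C30 question 16.
- These QLQ-C30 symptom items and the HADS are answered over the past week, so they support the description of symptoms but do not replace a 24-hour or present-moment score.

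**How far the trial had gone.** Section 14 refers to the first 32 patients of a planned 50, leaving 50 − 32 = 18. Some forms may therefore already exist. The documents do not say how many, or under which instruction they were completed.

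**The case against.** The strongest reply is that the two texts can coexist in practice. Section 2.3 promises an instruction to patients without distinguishing by mode, so staff could tell everyone to think of the last 24 hours and could have constipation written on the blank line. A blank with constipation printed as the prompt is compatible with that. This stands as a limit: mixing is possible, not established. It does not remove the conflict, because a patient given that instruction would still read a different one on the page, and no procedure makes either step happen.

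A reader might infer that hand-completed forms follow one recall period and phone forms the other. The documents do not support a split along that line; a staff member on the phone could equally read out the printed wording.

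A reader might also infer that objective 1.3.9 loses its only symptom measure. It does not. Section 2.3 lists nine symptoms in the QLQ-C30, including constipation. The ESAS-r is the instrument designated for symptoms, not the only one that records them.

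Finally, it may be said that the impact is small: a single-arm study, a descriptive secondary endpoint, and no ESAS-r threshold or decision rule. That is correct and sets the priority of the point.

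**Conclusion.** The point holds as a minor internal inconsistency. The plan gives two incompatible recall instructions for the instrument designated for symptom burden, and two incompatible specifications of item 10. ESAS-r scores can mix recall periods on all ten items, and item 10 can mix symptoms.

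The size of any shift in scores cannot be derived from the documents. The primary R0 resection endpoint, the sample size and the error rates do not depend on this.

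Two stronger conclusions should not be drawn. Item 10 is not unusable: wherever constipation was written, it can be summarised as constipation. Nor do the documents show that the printed wording is what enrolled patients followed, so they give no ground for preferring either recall period. If patients so far were told 24 hours, moving to the printed wording would itself introduce a change partway through the trial.

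The verdict assumes that the appended form is the one in use and that no separate instruction sheet or phone script, absent from these documents, already resolves the conflict.

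**What to change.** 1. Establish from the study team which recall instruction patients have received so far.
2. Make Section 2.3, the printed form and the wording used by phone agree on that one period.
3. For forms already collected, record the recall period and the mode of completion where these are known, and report them with the ESAS-r summaries.
4. Pre-print constipation in item 10 and in its worst-possible anchor.
5. Add to Section 14.3.6 that, on forms already collected, item 10 is summarised as constipation only where constipation was written.

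The cost is a minor amendment, which Section 13.1 requires to have IRB approval before implementation, and a check of the collected forms. Patients take on no extra burden.

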## **2.4 Health care utilization background**

As oncologists strive to improve care quality and lower health care costs, their focus has turned to reducing avoidable admissions and decreasing hospital length of stay (LOS) for patients with cancer.[42, 43] Patients with pancreatic cancer often experience symptoms related to the cancer itself or the therapies used to treat it.[32] Symptom management for these patients may necessitate frequent clinic visits, surgical interventions, and ultimately admissions to the hospital. Avoiding unnecessary hospitalizations is an area needing improvement for patients with cancer, but a better understanding of health care utilization is necessary in order to develop future interventions.[44] Thus, we propose to collect data on study participants' health care utilization including hospital admissions, intensive care unit stays and emergency room visits. Similar to measuring patient-reported outcomes, assessing health care utilization will help us better understand study patients' experience with their cancer treatment.

## **3 ELIGIBILITY CRITERIA**

### **3.1 Inclusion Criteria:**

Participants must meet the following criteria on screening examination to be eligible to participate in the study:

- 3.1.1 Cytologic or histologic proof pancreatic ductal carcinoma is required prior to study entry. Diagnosis must be confirmed by a DFHCC institution pathology department prior to registration.
- 3.1.2 No evidence of metastatic disease as determined by chest CT scan, abdomen/pelvis CT scan (or MRI with gadolinium and/or manganese). All patients must be staged with a physical exam, chest CT, abdominal CT with intravenous contrast (or Abdominal MRI with gadolinium and/or manganese).
- 3.1.3 Patients with locally advanced, unresectable disease will be included. Locally advanced unresectable disease is defined by the NCCN as:

- 1) Tumors of the head that have greater than 180 degrees of SMA encasement or any celiac abutment, unreconstructable SMV or portal occlusion, or aortic invasion or encasement.
- 2) Tumors of the body with SMA or celiac encasement of greater than 180 degrees, unreconstructable SMV or portal occlusion, or aortic invasion.
- 3) Tumors of the tail with SMA or celiac encasement of greater than 180 degrees.
- 4) Irrespective of location, all tumors with evidence of nodal metastasis outside of the resection field are deemed unresectable (6).

3.1.4 Patients must be 18 years old or older. There will be no upper age restriction.

3.1.5 ECOG-Performance Status of 0 or 1 are eligible.

3.1.6 Life expectancy of greater than 3 months.

3.1.7 Baseline SBP > 100mm Hg. This is based on the average of two values - separate seated, resting measurements taken five minutes apart. BP does not need to be checked in both arms unless a reading is below 110 mm Hg, in which case the other arm can be checked as well, If BP is checked in both arms, the higher value is deemed accurate for calculating the average.

3.1.8 Lab Values:

ANC  $\geq$  1500 cells/mm^3

Platelet count  $\geq$ 100,000 cells/mm^3.

AST and ALT  $\leq$  2.5 x upper limit of normal OR two downtrending values

Total Bilirubin  $\leq$  1.5 x upper limit of normal if no biliary stenting has been done;

OR 2.0 x upper limit of normal if patient is s/p biliary stenting;

OR two downtrending values

**Serum Creatinine  $\leq$  1.5 mg/dl** Creatinine Clearance  $\geq$  30ml/min (as estimated by Cockcroft Gault Equation):

$$\text{Creatinine clearance for males} = \frac{(140 - \text{age [yrs]}) (\text{body wt [kg]})}{(72) (\text{serum creatinine [mg/dL]})}$$

Creatinine clearance for females = 0.85 x male value

- 3.1.9 The effects of radiation on the developing human fetus are known to be teratogenic. Women of child-bearing potential and men must agree to use adequate contraception (hormonal or barrier method of birth control; abstinence) prior to study entry and for the duration of study treatment plus 30 days from the last date of study drug administration. Should a woman become pregnant or suspect she is pregnant while participating in this study, she should inform her treating physician immediately.
- 3.1.10 Ability to understand and the willingness to sign a written informed consent document.

